7.3 Duration of Participation

The individual's participation will only be for the duration of the CTA examination.

7.4 Test Article(s) (Study Drug(s) and/or Study Device(s))

7.4.1 Description

Intravenous contrast, Omnipaque, will be administered as described above. The intravenous contrast is FDA approved for use of CTAs and is a standard of care practice at PSHMC with the standard contrast dose of 100 mL.

7.4.2 Treatment Regimen

At this institution, CTAs are performed with the standard contrast dose of 100 mL. This study will administer intravenous contrast, Omnipaque, at a dosage of 40 mL at a rate of 5mL/sec or at 50 mL at a rate of 5mL/sec as described above.

- 7.4.3 Method for Assigning Subject to Treatment Groups Not Applicable
- 7.4.4 Subject Compliance Monitoring Not Applicable
- 7.4.5 Blinding of the Test Article Not Applicable

7.4.6 Receiving, Storage, Dispensing and Return

7.4.6.1 Receipt of Test Article

The intravenous contrast, Omnipaque, will be received according to standard practice of the institution

7.4.6.2 Storage

The intravenous contrast, Omnipaque, will be stored according to standard practice of the institution.

7.4.6.3 Preparation and Dispensing

The intravenous contrast, Omnipaque, will be prepared and administered as per standard of care procedures.

7.4.6.4 Return or Destruction of the Test Article

Not Applicable

7.4.6.5 Prior and Concomitant Therapy

Not Applicable

8.0 Subject Numbers and Statistical Plan

8.1 Number of Subjects

The number of study subjects anticipated is 180 patients.

8.2 Sample size determination

This number of patients achieves 80% power, with a 7.5% equivalence margin, at a 5% significance level using a two-sided equivalence test of correlated proportions when the actual difference of the proportions is zero.

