1.0 Objectives

1.1 Study Objectives

The purpose of the study is to determine if the dose of contrast administered for computed tomographic arteriograms (CTA) can be reduced without degradation of image quality. The hypothesis is that there is no difference in image quality using ultra-low dose contrast in CTA exams compared to routine dose exams.

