1.2 Primary Study Endpoints

The objective is to prospectively evaluate image quality of CTA examinations performed with an ultralow contrast dose protocol. The primary endpoint would be to show that there is no statistical difference in the quality of the images.

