8.3 Statistical methods

Measured data from CTAs performed with low intravenous contrast dose and from CTAs performed with routine intravenous contrast dose for each patient will be analyzed using paired t-tests. The statistical methodology will be reviewed by consultation with biostatistics.

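### The purpose is one-directional (no degradation), but the hypothesis, endpoint and sizing test are two-directional, so a large enough gain for low dose would miss the criterion

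*Combined protocol and SAP*

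**What the plan says.** Section 1.1 contains two statements that point in different directions. The purpose is to find out whether the contrast dose "can be reduced without degradation of image quality". The hypothesis, in the next sentence, is that "there is no difference in image quality using ultra-low dose contrast in CTA exams compared to routine dose exams".

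The later sections follow the hypothesis:

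- Section 1.2: "The primary endpoint would be to show that there is no statistical difference in the quality of the images".
- Section 8.1: "The number of study subjects anticipated is 180 patients".
- Section 8.2: "This number of patients achieves 80% power, with a 7.5% equivalence margin". The level is given only as 5%, and the calculation is described as made "using a two-sided equivalence test of correlated proportions when the actual difference of the proportions is zero".
- Section 8.3: measured data from the two scans "for each patient will be analyzed using paired t-tests", with no margin and no direction.

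No section says how a result favouring low dose would be read, or why better images should count against it.

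**The concern.** If the question is whether quality is lost, only the lower side of the comparison matters. A two-sided equivalence rule also requires the upper confidence limit to stay below +7.5 points, and a no-difference endpoint is missed by a significant gain. Either rule can return a failure when the purpose in 1.1 has been met.

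A gain cannot be excluded under this plan. The low-dose scan is always the later of the pair, and the routine scan may be up to two years old (4.2). A team member supervises the low-dose scan, which 7.2.1 names as a difference for the patient. In high-pitch mode the scan delay is lengthened by 2 seconds (7.1). The documents do not indicate how large any gain might be.

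This is separate from the difference test in 8.3. Replacing the t-tests with the equivalence test of 8.2 would still leave the upper side in the success rule.

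**Working it through.** **Inputs.** N = 180 pairs (8.1). Margin m = 7.5%, read as percentage points; 80% power; 5% significance level; true difference zero (all 8.2). The plan does not give the proportion of discordant pairs (ψ), the success proportion, or whether 5% is the level of each one-sided test or is split into 2.5% per side. Both readings are used. Normal quantiles: 1.645 (5%), 1.960 (2.5%), 1.282 (90%).

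**1. Reproduce 8.2.** At zero difference SE = √(ψ/N), and equivalence power = 2Φ(m/SE − z) − 1. Power of 80% requires m/SE = z + 1.282.

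- 5% per side: SE = 7.5/(1.645 + 1.282) = 2.56 points; ψ = 180 × 0.0256² = 0.118.
- 2.5% per side: SE = 7.5/(1.960 + 1.282) = 2.31 points; ψ = 180 × 0.0231² = 0.096.

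Simulated power at these values was 79% and 78%. So 180 is attainable, but it cannot be confirmed because ψ is not stated.

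**2. How large an observed gain misses the criterion?**

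- Equivalence, 5% per side: above 7.5 − 1.645 × 2.56 ≈ 3.3 points.
- Equivalence, 2.5% per side: above 7.5 − 1.960 × 2.31 ≈ 3.0 points.
- No statistical difference (two-sided 5% test, ψ = 0.118): above 1.960 × 2.56 ≈ 5.0 points.

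Smaller gains pass.

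**3. Power if low dose is truly better by δ.** SE = √((ψ − δ²)/N). Equivalence power = Φ((m − δ)/SE − z) − Φ(−(m + δ)/SE + z). Non-inferiority power = Φ((m + δ)/SE − z). For example, with ψ = 0.1182, δ = 0.025 and 5% per side, SE = 0.02556. Equivalence power is Φ(0.311) − Φ(−2.267) = 0.622 − 0.012 = 0.61. The values of δ are assumptions.

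| True gain (points) | Equivalence, ψ 0.118, 5% per side | Non-inferiority, same ψ and level | Equivalence, ψ 0.096, 2.5% per side | Non-inferiority, same ψ and level |
|---|---|---|---|---|
| 0 | 80% | 90% | 80% | 90% |
| 2.5 | 61% | 99% | 57% | 99% |
| 5 | 25.5% | 99.9% | 19% | about 100% |
| 7.5 | 5% | about 100% | 2.5% | about 100% |

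**4. Non-inferiority power at 180 pairs, zero true difference.** Power = Φ(m/SE − z).

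- ψ = 0.118, one-sided 5%: Φ(7.5/2.56 − 1.645) ≈ 90%.
- ψ = 0.118, one-sided 2.5%: Φ(7.5/2.56 − 1.960) ≈ 83%.
- ψ = 0.096, one-sided 2.5%: Φ(7.5/2.31 − 1.960) ≈ 90%.

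**5. Sensitivity to ψ.** At ψ = 0.15, equivalence power (5% per side) is 66%. Non-inferiority power is 83% (one-sided 5%) or 74% (one-sided 2.5%). At ψ = 0.20 the figures are 46%, 73% and 61%. Power therefore depends heavily on a quantity that the plan does not state.

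**The case against.** The strongest defence is that 8.2 matches the stated hypothesis. Section 1.1 proposes no difference, and 1.2 and 8.2 test that in both directions. This stands. It places the conflict inside 1.1, between purpose and hypothesis, and does not remove it.

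A reader might infer that any better score for low dose counts as failure. The documents do not support that: at the back-solved discordance, gains up to about 3 points still pass. A reader might also infer that a positive result would be invalid or would leave the question unanswered. It would not, because passing two-sided equivalence shows non-inferiority at the same margin and level.

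A gain is also uncertain. Low dose uses 40 to 50 mL against 100 mL. Section 2.2 reports preliminary data with no difference in opacification or rated quality, and 7.1 keeps other imaging parameters unchanged. This stands: the true gains in the table are assumptions and not forecasts.

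Finally, a gain from supervision or timing would not be an effect of contrast volume, and an upper bound would flag it. That is a fair reason to keep looking at the upper limit, and reporting it descriptively does so. It is a weak reason to make it a condition of success: a dose-related loss offset by better supervision would appear as zero difference and pass either test.

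**Conclusion.** The point holds in a limited form, as an inexpensive improvement. The purpose is one-directional; the hypothesis, endpoint and sizing test are not. The error rate for a false claim of no degradation is unaffected. What is lost is power, 80% against 90% at zero difference under the same ψ and per-side level and more if low dose is truly better, together with a clear reading of a favourable result.

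The size rests on three assumptions: 7.5% means percentage points, all 180 pairs are evaluable, and ψ is 11.8% or 9.6% according to how the 5% in 8.2 is read. Neither ψ is documented. The 90% figure should therefore not be taken as an established property of 180 patients: at ψ = 11.8% and one-sided 2.5% it is 83%.

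**What to change.** State one direction in 1.1, 1.2 and 8.2, and carry it into 8.3:

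- **1.1 and 1.2:** reword the hypothesis and endpoint as low-dose image quality not being worse than routine by 7.5 points or more.
- **8.2:** define success as the lower confidence limit for low-dose minus routine (paired proportions) lying above -7.5 points. State the one-sided alpha and the assumed discordance, and label the power as conditional on them. If 8.2 already means 2.5% per side, keep that level; moving to 5% would loosen the error rate.
- **8.3:** replace the paired t-test for this endpoint with that confidence limit, and report the upper limit descriptively. Without this change the new rule has no effect. It also needs a definition of which Likert scores (7.1) count as success, since 8.2 refers to proportions and no cut-off is given.

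If the investigators prefer equivalence, they should say why better images should count against low dose.

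The cost is wording. At the back-solved discordances, no extra patients, scans or reads are needed. The small downside is that the trial could claim only that low dose is not worse, and not that the two doses are the same in both directions.

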8.3 Statistical methods

Measured data from CTAs performed with low intravenous contrast dose and from CTAs performed with routine intravenous contrast dose for each patient will be analyzed using paired t-tests. The statistical methodology will be reviewed by consultation with biostatistics.

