7.0 Study Design and Procedures

7.1 Study Design

Any adult patient scheduled for routine CTA meeting the inclusion/exclusion criteria and providing consent will be included in the study. The patient will be administered a low dose of intravenous contrast based on the study examination as described below. The contrast agent being used is Omnipaque. The scan will be performed under the supervision of the primary investigator or the described team members to make sure that the study is of diagnostic quality.

The following dose protocols will be followed:

CTA of the chest: 40 mL of intravenous contrast at a rate of 5mL/sec. A region of interest (ROI) to trigger the scan will be placed in the aortic arch. If scan is performed using high pitch helical mode, the scan delay will be increased by 2 seconds.

CTA of the abdomen OR or CTA of the chest and abdomen or CTA of the abdomen and pelvis or CTA of the chest, abdomen and pelvis: 50 mL of intravenous contrast at a rate 5mL/sec. A region of interest (ROI) to trigger the scan will be placed in the aortic arch. If scan is performed using high pitch helical mode, the scan delay will be increased by 2 seconds.

All other imaging parameters will remain unchanged, given that the subjects enrolled will be clinical patients of the principle investigator.

Following the examination, the primary investigator (PI) or team members will evaluate the images obtained with low contrast dose and each patient's prior CTA examination performed with routine contrast dose. This will be done by quantitative and qualitative measures. For the quantitative portion, the PI or team members will place regions of interest on predetermined arterial locations to obtain measure the degree of opacification. For qualitative measurement, the images will be presented in a blind fashion to two thoracic trained board certified radiologists and a board certified interventional radiologist to determine the quality of the images based on a Likert numerical scale. Qualitative and quantitative data for the images obtained with low contrast dose and those for the prior CTA examinations performed with routine contrast dose will be compared. This data along with details of the

scan protocol (dose, dose rate, scanning parameters etc.) and demographic data (such as sex, age and BMI at the time of examination) will be recorded in Redcap.

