11.0 Risks

There is a minimal risk of loss of confidentiality.

There is a risk of increased radiation if the scan needs to be repeated due to a non-diagnostic clinical exam. If the exam is non-diagnostic due to inadequate vascular enhancement, the examination will be repeated. This may lead to an increased radiation dose to the patient. It is important to note that non-diagnostic studies can, and do occur with the standard volume of contrast currently administered for these examinations. When this occurs, the examination is repeated with a second standard or reduced dose of contrast. Given the low dosage of intravenous contrast of the planned low dose protocol, a repeat examination can be performed without exceeding the standard of care contrast dose to the patient,

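### The trial is sized on an equivalence test of paired proportions, but section 8.3 tests only means, so the share of inadequate scans is never defined or analysed

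*Combined protocol and SAP*

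**What the plan says.** - **Aim (section 1.2).** "The primary endpoint would be to show that there is no statistical difference in the quality of the images". No summary measure is named.
- **Measurements (section 7.1).** Team members will "place regions of interest on predetermined arterial locations to obtain measure the degree of opacification", and three radiologists will "determine the quality of the images based on a Likert numerical scale". Neither measure has a cut-off for an adequate scan.
- **Failure (section 11.0).** "If the exam is non-diagnostic due to inadequate vascular enhancement, the examination will be repeated". This describes the failure in words, with no threshold and no expected rate. Section 7.2.1 also provides for a repeat scan. Neither section says which acquisition enters the comparison after a repeat.
- **Sample size (sections 8.1 and 8.2).** "The number of study subjects anticipated is 180 patients", justified "with a 7.5% equivalence margin, at a 5% significance level" and "using a two-sided equivalence test of correlated proportions when the actual difference of the proportions is zero". The yes/no outcome behind those proportions is not stated.
- **Analysis (section 8.3).** Measured data from the low-dose scans and from those at "routine intravenous contrast dose for each patient will be analyzed using paired t-tests". No other analysis is named, although a consultation with biostatistics is foreseen.
- **Monitoring (sections 10.1 and 10.7).** Section 10.7 says the statistical tests are those of 8.2 and 8.3. Repeat scans are named as a reported item only in the summary of the first 20 patients for the IRB.

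**The concern.** Sections 8.2 and 8.3 answer different questions. The first asks whether the share of patients with some quality attribute is the same at both doses, to within 7.5 points. The second asks whether the average differs.

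Whether the low-dose protocol is usable depends heavily on how often an individual scan is inadequate. A mean lets a gain in one patient cancel a loss in another, even when the gain is from good to better and the loss is from adequate to inadequate. Putting an equivalence margin on the mean would not remove this limitation.

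At stake is a report of unchanged image quality that contains no test of whether more patients had an inadequate scan, from a trial whose size was chosen for such a test.

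**Working it through.** **1. The plan's own figure.** For two one-sided tests on paired proportions with true difference zero, N = p_disc × (z_α + z_(1−β/2))² / margin², where p_disc is the proportion of discordant pairs. The documents give N = 180, margin 0.075, 80% power and a 5% level. They do not give p_disc, so 180 can only be solved backwards.

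- 5% per side: (1.645 + 1.282)² / 0.075² = 1,522, so p_disc = 180 / 1,522 = 11.8%.
- 2.5% per side: (1.960 + 1.282)² / 0.075² = 1,868, so p_disc = 180 / 1,868 = 9.6%.

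The number is attainable, but it cannot be checked without the assumed discordance and the outcome it refers to.

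**2. Equal means, wider spread.** The documents give no SD, correlation, threshold or failure rate, so everything in steps 2 to 4 is assumed. With normal data and a threshold that a proportion p of routine scans fall below, the low-dose share is Φ(z(p) / r), where r is the ratio of low-dose to routine SD. For p = 5% and r = 1.5: Φ(−1.645 / 1.5) = Φ(−1.097) = 13.6%, a rise of 8.6 points.

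| Routine share | r = 1.25 | r = 1.5 | r = 2.0 |
|---|---|---|---|
| 1% | 3.1% (+2.1) | 6.1% (+5.1) | 12.2% (+11.2) |
| 2% | 5.0% (+3.0) | 8.6% (+6.6) | 15.2% (+13.2) |
| 5% | 9.4% (+4.4) | 13.6% (+8.6) | 20.5% (+15.5) |
| 10% | 15.3% (+5.3) | 19.6% (+9.6) | 26.1% (+16.1) |

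Rises in brackets are in percentage points. Whether the rise exceeds 7.5 points depends on both assumed inputs.

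**3. What each test does in the 5.0% to 13.6% case.** These are 20,000 simulated trials of 180 pairs at each within-patient correlation of 0.3, 0.5 and 0.7.

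- Paired t-test rejects: about 5%, its nominal level.
- McNemar test on the yes/no outcome rejects: 87% to 95%.
- Paired-proportion equivalence test, margin 7.5 points, 5% per side, wrongly declares equivalence: about 2.6%.

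**4. When the mean is not preserved.**

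- The same 5.0% to 13.6% rise produced by a shift of 0.55 SD: the t-test rejects in essentially all trials.
- 10% to 20% of low-dose scans drop by 1.5 to 2.5 SD with no offsetting gain, giving 12% to 13% inadequate: the t-test rejects in 67% to 99%.
- Likert example: routine scores 3/4/5 in 15/50/35% of patients, 8% of patients fall to score 2, and a fraction u of the remaining scores below 5 rise one step. The mean change is −0.08 × (0.15×1 + 0.50×2 + 0.35×3) + 0.92 × 0.65 × u = −0.176 + 0.598u. The t-test rejects in over 99% of trials at u = 0, 91% at 5%, about 64% at 10%, 34% at 15%, 14% at 20% and 5% at 28%. The share scoring below 3 rises by 8 points in every case.

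The t-test therefore loses the signal gradually as gains offset losses. It is blind only near exact cancellation.

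**The case against.** The strongest reply is that near-cancellation is a special case. Nothing in the documents shows that the low dose widens the spread while leaving the mean alone. Section 7.1 has supervision in place to secure a diagnostic scan and says the other imaging parameters stay as they are; neither implies that typical enhancement will rise. Symmetric widening at an unchanged mean would also require more very bright scans on less contrast. Failures caused by generally weaker enhancement would move the mean, and the t-test would find them. All of this stands, and it limits the point to a conditional one.

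A second reply is that the proportion test is already in the plan, since section 10.7 refers to 8.2 as well as 8.3. This stands only in part. The method is named, but without a defined yes/no outcome it cannot be run, and the section on statistical methods does not include it.

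A reader might infer that paired t-tests cannot detect a rise in inadequate scans at all, or that the low dose is expected nearly to triple them. The documents support neither. Step 4 of the working contradicts the first. The 2.7-fold rise (13.6 / 5.0) comes from an assumed baseline and SD ratio, and at a 2% baseline the same ratio gives +6.6 points, inside the plan's own margin. Nor does section 11.0 define a failure threshold; it only describes the event.

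**Conclusion.** The point holds in conditional form. What is certain from the text is that 8.2 and 8.3 do not match, that no yes/no image-quality outcome is defined, and that following 8.3 as written never tests the share of inadequate scans.

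The consequence depends on how the low dose acts. If the spread widens and the mean is nearly preserved, the t-test rejects at about its 5% level while the share can rise beyond 7.5 points; the 5.0% to 13.6% example rests on normality, equal means, a 5% baseline and an SD ratio of 1.5. If the mean falls, or some patients lose quality without offsetting gains elsewhere, detection with 180 pairs is usually good. The point should be acted on because the mismatch is plain and the repair is cheap, not because a hidden excess of failures has been shown to be likely.

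**What to change.** In section 8.3:

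1. Make the paired-proportion equivalence test of 8.2, with its 7.5% margin, the primary analysis.
2. Define the yes/no adequacy outcome before any scan is read: a cut on the Likert scale, with a rule for combining the three readers, and an HU threshold. State which of the two carries the primary test.
3. For HU, use the lowest value among the predetermined sites covered by both of the patient's scans. Chest-only and abdomen-only examinations are both eligible, so a single site need not be available in every patient, while this rule gives one pair per patient with a shared site. Restricting to shared sites matters because a scan with wider coverage would otherwise tend to have the lower minimum.
4. Analyse the first low-dose acquisition even when the scan is repeated; otherwise the failures drop out of the proportion. State the corresponding rule for the prior scan, since section 11.0 says routine-dose scans are sometimes repeated too.
5. Report the discordant counts in both directions, and state in 8.2 the discordance that 180 assumes.
6. Keep the paired t-tests on means as supportive.

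The cost is a change of wording and one or two derived variables from data already collected, provided the first acquisition is kept and read. The downside is that a yes/no outcome is less sensitive to a small uniform shift, which the supportive comparison of means covers.

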1.3 Secondary Study Endpoints

Not Applicable

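### Section 8.3 runs unranked paired t-tests on several image-quality measures and does not say which result decides the single endpoint, or how it relates to the equivalence test in 8.2

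*Combined protocol and SAP*

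**What the plan says.** Section 1.2 states: "The primary endpoint would be to show that there is no statistical difference in the quality of the images". Section 1.3 marks secondary endpoints as not applicable, so no quality measure ranks below another.

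Section 7.1 describes two kinds of assessment per scan. For the qualitative part, blinded images go to "two thoracic trained board certified radiologists and a board certified interventional radiologist", who "determine the quality of the images based on a Likert numerical scale". The number of scale points, any cut-off and any rule for combining the three readers are not given. For the quantitative part, the team will "place regions of interest on predetermined arterial locations"; their number and identity are not given. Both kinds of data are then to be compared between the low-dose scan and the patient's earlier routine-dose scan.

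Section 8.3 says that measured data from the two scans of each patient "will be analyzed using paired t-tests", and adds that biostatistics will be consulted on the methodology. It names no primary variable, significance level, margin or multiplicity rule.

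Section 8.2 justifies 180 patients by a two-sided equivalence test of correlated proportions: 80% power, a 7.5% margin, a 5% level and a true difference of zero. It does not say what the proportion is. Section 10.7 refers to both 8.2 and 8.3 for the statistical tests.

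**The concern.** The plan does not determine what result counts as success. Three sets of reader scores and at least two sets of Hounsfield values fall under one endpoint, and they can disagree. If a difference on any of them counts against the low dose, an adequate protocol may be rejected by chance. If one of them settles the matter, the plan does not say which, and the conclusion could rest on whichever is quoted.

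The form of the test adds to this. The trial was sized to show equivalence within a margin, but a paired t-test as described in 8.3 asks whether a difference can be detected. Failing to detect one does not establish that the difference is small enough, however many measures are tested.

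**Working it through.** **Inputs from the documents.** 180 pairs (8.1); margin 0.075, power 0.80, level 0.05, true difference 0 (8.2); 3 readers and more than one arterial site (7.1).

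**Assumptions.** Two sites, the fewest that the plural allows, with larger counts as a range; each test two-sided at 5%; equal correlation between test statistics, from 0 to 0.9. None of these is in the documents.

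**1. The plan's own figure.** For two one-sided tests on paired proportions with true difference zero, n = (z(1−α) + z(1−β/2))² × pd / margin², where pd is the proportion of discordant pairs. The plan does not give pd, so it is solved from n = 180:

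- α = 0.05 per side: pd = 180 × 0.075² / (1.645 + 1.282)² = 1.0125 / 8.564 = 11.8%.
- α = 0.025 per side: pd = 1.0125 / (1.960 + 1.282)² = 1.0125 / 10.507 = 9.6%.

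So 180 is plausible for one matched binary outcome per patient, but it cannot be confirmed. At pd = 15% the same formula needs 229 (α = 0.05 per side) or 281 (0.025 per side).

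**2. Several unranked tests with no true difference.** With k independent tests, the chance of at least one false difference is 1 − 0.95^k. For five tests, 1 − 0.95⁵ = 22.6%. Correlated values come from simulation (400,000 draws of equicorrelated normal statistics):

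| Tests | Correlation 0 | 0.5 | 0.7 | 0.9 |
|---|---|---|---|---|
| 5 (3 readers + 2 sites) | 22.6% | 18.2% | 15.0% | 10.2% |
| 6 (3 + 3) | 26.5% | 20.8% | 16.4% | 10.9% |
| 8 (3 + 5) | 33.7% | 24.9% | 19.1% | 11.9% |
| 13 (3 + 10) | 48.7% | 33.3% | 24.0% | 13.7% |

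**3. Non-significance is not equivalence.** As an illustration, take the binary outcome with pd = 11.8%, and ignore the small effect of the observed difference on its variance. The standard error is √(0.118/180) = 0.0256.

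- A difference test at 5% is non-significant when the observed difference is below 1.96 × 0.0256 = 5.0 points.
- The equivalence test at 0.05 per side succeeds only when it is below 7.5 − 1.645 × 2.56 = 3.3 points.

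An observed difference between 3.3 and 5.0 points would therefore count as no statistical difference and yet fail the test that sized the trial. For Likert scores or Hounsfield values no margin is stated at all, so a t-test on them cannot be read as an equivalence result.

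**The case against.** The strongest reply is that 8.3 need not cover everything. Section 10.7 lists the 8.2 test among the tests to be used. One sensible reading is that reader scores, turned into proportions, go to the equivalence test and only Hounsfield values go to t-tests. A reader might infer that all scores and measurements go into t-tests, but 8.3 speaks only of measured data and does not say so. This part of the reply stands. It does not close the gap: the proportion, the Likert cut-off and the reader rule would still be undefined, and nothing says which result decides. On that reading, two independent Hounsfield tests at 5% would still give 1 − 0.95² = 9.8%.

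A reader might also infer that the three reads are stacked as 540 independent rows, so that errors are understated and equivalence is claimed too easily. The documents do not support this. Section 8.3 pairs data patient by patient, and no section describes pooling reads. Moreover, under t-tests too small a standard error produces more differences, not easier equivalence.

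Two further points are fair. The arterial sites are fixed in advance, which limits later choice of vessel. And if success requires no difference on any measure, multiplicity works against the trial's own hypothesis. That rules out a multiplicity correction alone as the remedy, since it would make no difference easier to declare. The promised biostatistics consultation has no content yet and settles nothing.

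**Conclusion.** The concern holds as a failure to name the deciding analysis. This is certain from the text: one endpoint, several measures, paired t-tests in 8.3, an equivalence test in 8.2, and no ranking between them in 10.7.

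The size is conditional. Five separate tests at 5% give about a 15 to 23% chance of at least one false difference for correlations of 0.7 down to 0, and about 10% at 0.9. More sites raise it. The level, the number of sites and the correlations are assumptions, as is the separate testing of each reader. The point that non-significant t-tests cannot show equivalence within 7.5 points depends on none of them.

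**What to change.** In 8.3, name one deciding analysis, and align 1.2, 1.3 and 10.7 with it.

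- **Primary.** Combine the three reads into one value per scan, for example the two-of-three majority for adequate quality, with the Likert cut-off fixed before unblinding. This gives 180 matched pairs. Test them with the equivalence test of correlated proportions from 8.2 at the 7.5-point margin, and state the level per side.
- **Secondary.** Analyse Hounsfield values in a mixed model with dose and location as fixed effects and patient and scan-within-patient as random effects, or analyse within-patient differences by location. The scan effect is needed because sites in one scan share a contrast bolus.
- **Descriptive.** Report each reader's results and inter-reader agreement. If reads are ever pooled, account for clustering by patient.

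The cost is mainly wording and a little more analysis, with no extra readers. Dichotomising loses some detail, which the descriptive results retain. The 80% power holds only if discordance of the combined read is about 10 to 12%. The plan should state its assumed discordance, because a higher value would call for more than 180 patients or lower power.
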